### **6.3. ACCOUNTABILITY OF NTRA-9620**

NTRA-9620 will be supplied in stick packs, in quantities as needed to comply with the treatment of site subjects according to the study protocol.

The initial study drug supply will be shipped after site activation (i.e., after the Sponsor has received all required regulatory documentation and a contract has been executed). The initial study drug shipment will include a specified number (baseline quantity) of study drug kits for each treatment arm. However, since both doses of NTRA-9620 and the matching placebo are packaged and labeled in a blinded manner, the study sites will not be able to distinguish among the three (3) different study drug types and will treat all study drug kits in the same manner.

Subsequent study drug shipments will be made when the inventory level for any study drug type (NTRA-9620 low dose, NTRA-9620 high dose, or matching placebo) reaches its alert quantity. In this case, the electronic randomization and drug supply system generates a shipment request in order to bring the site's inventory of all study drug types to their baseline quantity.

Shipment, storage, and inventory documentation will be updated regularly and kept in the investigation files at the site to allow inspection and trace of the supplied product.

*Used investigational product:* Used/opened stick packs will be destroyed.

All unused stick packs must be returned to the Sponsor after accountability records have been confirmed by the study monitor. Accountability of the study medication must include reconciliation of any unused stick packs not returned.

## 7. SAFETY MONITORING AND ADVERSE EVENTS

### 7.1. ADVERSE EVENTS

Data regarding treatment-emergent AEs will be collected. Treatment-emergent AEs are events that are not present at baseline or, if present at baseline, have worsened in severity or frequency.

If applicable to this study population, the descriptions and grading scales found in the Common Terminology Criteria for Adverse Events (CTCAE) v 4.03 will be used for AE reporting. For events where the specific definitions for grading in CTCAE does not apply to this study population, general grading criteria described in CTCAE will be used and investigator judgment on severity will determine the grade of the event. See [Appendix C](#) for link to a copy of CTCAE v 4.03.

#### 7.1.1. Definition of Adverse Events

##### **Adverse Event (AE)**

An adverse event (AE) is any untoward medical occurrence in a clinical investigation of a subject administered a pharmaceutical product (either test product or control product); an AE does not necessarily have a causal relationship with the treatment. An AE is therefore any unfavorable and unintended sign, symptom, or disease temporally associated with the use of an investigational (medicinal) product or other protocol-imposed intervention, regardless of attribution, i.e., whether or not related to that investigational (medicinal) product. An AE may include intercurrent illnesses or injuries that represent an exacerbation (increase in frequency, severity, or specificity) of pre-existing conditions (e.g., worsening of asthma). A laboratory abnormality will be reported on the “Adverse Event” case report form only if the investigators considered it clinically significant, or if it is associated with clinical sequelae or requires therapeutic intervention.

##### **Adverse Drug Reaction (ADR)**

Any AE for which there is a reasonable possibility that the study drug caused the adverse event, means there is evidence to suggest a causal relationship between the study drug and the adverse event, or that a causal relationship between a study drug and an adverse event is at least a reasonable possibility, i.e., the relationship cannot be ruled out. The relationship may be ruled as unlikely, possibly or probably related to study drug – see definitions below.

##### **Unexpected AE**

An unexpected AE is one of a type not identified in nature, severity, or frequency in the current Investigator’s Brochure or of greater severity or frequency than expected based on the information in the Investigator’s Brochure.

A pre-treatment emergent event will not be considered an AE, but will be recorded as medical history.

Whenever possible, it is preferable to record a diagnosis as the AE term rather than a series of symptoms relating to a diagnosis. AEs will be graded according to the CTCAE v 4.03 ([Appendix C](#)). For events where the specific definitions for grading in CTCAE does not apply to this study population, general grading criteria described in CTCAE will be used and investigator judgment on severity will determine the grade of the event.

AEs monitoring will be captured throughout the study, from Day 0 (initiation of dosing) until final primary study visit at Week 28 (Day 196). Long-term safety evaluations will also be conducted post primary study completion on Week 52 (Days 364) and Week 104 (Day 728) to assess any potentially related adverse outcomes of treatment.

If an unrelated AE remains unresolved after Week 28, at the Investigator's discretion, the subject may be followed until Week 104, or until resolution of the event. The investigators must follow a related AE and any unrelated/related SAE until resolution even if the time extends beyond the study-reporting period. Resolution is defined as the return to baseline status or stabilization of the condition with the expectation that it will remain chronic; it is not a discharge date from the hospital.

The investigator will assess AEs for severity, for relationship to the study drug, and as to whether the event meets one or more of the definitions of an SAE.

The investigator will determine the relationship of an AE to the study drug and will record it on the source documents and AE CRF, using the categories defined below.

Causality Category	Description
Unlikely	A clinical event, including laboratory test abnormality, with a temporal relationship to drug administration which makes a causal relationship improbable, and in which other drugs, chemicals or underlying disease provide plausible explanations. For the purpose of this protocol, the term unlikely will be considered not related to study medication and an "Adverse Event".
Possible	A clinical event, including laboratory test abnormality, with a reasonable time sequence to administration of the drug, but which could also be explained by concurrent disease or other drugs or chemicals. Information on drug withdrawal may be lacking or unclear. For the purpose of this protocol, an event that has possible relationship to study medication will be defined as a "Suspected Adverse Drug Reaction".
Probable	A clinical event, including laboratory test abnormality, with a reasonable time sequence to administration of the drug, unlikely to be attributed to concurrent disease or other drugs or chemicals, and which follows a clinically reasonable response on withdrawal. For the purpose of this protocol, an event that has probable relationship to study medication will be defined as an "Adverse Drug Reaction".

In order to classify adverse events and diseases, the sponsor or its designee will assign preferred terms to the original terms entered on the CRF, using the Medical Dictionary for Regulatory Activities (MedDRA).

AEs will be graded on a 5-point scale (mild, moderate, severe, life-threatening, and death) and reported as indicated on the CRF. Intensity of adverse event is defined as follows:

**Table 2: Severity Assessment Terminology for Reporting Adverse Events**

CTCAE Grade	Common Term	Description
1	Mild	Mild; asymptomatic or mild symptoms; clinical or diagnostic observations only; intervention not indicated
2	Moderate	Moderate; minimal, local or noninvasive intervention indicated; limiting age-appropriate instrumental Activities of Daily Living (ADL)
3	Severe	Severe or medically significant but not immediately life-threatening; hospitalization or prolongation of hospitalization indicated; disabling; limiting self-care ADL
4	Life-threatening	Life-threatening consequences; urgent intervention indicated
5	Death	Outcome of AE was death

AEs that are not described on the CTCAE v 4.03 will be graded according to the scale defined in [Table 2](#).

## 7.2. SERIOUS ADVERSE EVENTS

According to the ICH Guidelines for Good Clinical Practice (GCP) (E6), an SAE is any untoward medical occurrence during the course of a clinical investigation that is characterized by one or more of the following:

- Results in death
- Is life-threatening
- Requires in-subject hospitalization or prolongation of existing hospitalization
- Results in persistent or significant disability/incapacity
- Important medical events

### 7.2.1. SAE Reporting

All SAEs must be promptly reported to the Sponsor by the Investigator, study coordinator, other designated study personnel, or clinical research associate within 24 hours of notification of the SAE for related SAEs and within 48 hours for unrelated SAEs. To report such events, the

Investigator must complete an SAE form and send it within 24 hours by email or fax with relevant information.

Within the 48 hours following the initial report, the Investigator must provide further information on the SAE. This should include a copy of the completed SAE form, and any other information that will assist the understanding of the event. Significant new information on ongoing SAEs will be provided promptly as a follow-up.

The Investigator also must report all SAEs promptly to the appropriate IRB/IEC as required by the IRB/IEC.

#### 7.2.2. Recording of Serious Adverse Events

All SAE information must be recorded on the SAE form provided by the Sponsor. Additional follow-up information (e.g., test results, autopsy report, discharge summary, and CRF pages for AEs, concomitant medications, study drug administration, and medical history) must be obtained to supplement the SAE report form. A copy of all initial and follow-up reports must be filed with the subject's CRF.

### 8. STATISTICAL CONSIDERATIONS

#### 8.1. OVERVIEW

The aim of this study is to evaluate the safety and efficacy of NTRA-9620 relative to matching placebo on intestinal failure due to SBS. Safety will be assessed by AEs while primary efficacy will be assessed by change in parenteral feeding.

This section briefly describes the analyses planned for the trial. A full statistical analysis plan (SAP), to be written while the study is still blind, will describe the methods in detail. Should the SAP and this protocol not be in complete agreement, the methodology in the SAP will prevail.

### **8.1.1. Interim Check of Variance Assumption**

This multicenter trial will allow inclusion of a large population of infants from preterm to one year, SBS of varying etiologies, bowel length of varying sizes, presence or absence of ileocecal valve, and varying feeding regimes (e.g., formula only, full or partial own mother's milk). We know of no similar study that has been conducted in such a wide-ranging population - a population that is expected to have especially high variation with respect to prognosis and therefore to study outcome. Our best estimate of within-group variation, which is critical for accurately computing study power, is based on a small pilot study in a related, but not identical, indication. Consequently, we will assess the assumptions used for calculating power by computing the common pooled standard deviation of percent change in %PN when 75 subjects have completed 12 weeks in the study. Should the calculated standard deviation be at least 22% (i.e., 10% greater than the 20% assumed in the protocol), sample size may be adjusted upward accordingly. A statistician blinded to group assignment will compute this interim standard deviation. That statistician will not be involved in any other aspect of the trial. The sponsor will decide whether to increase the sample size during the trial; the decision will be based on the estimated variance but without any knowledge of the interim effect size.

### **8.1.2. Statistical Tests of Co-Primary and Key Secondary Endpoints**

#### **Co-Primary Endpoint (means)**

The two endpoints (12 weeks and 24 weeks) will each be analyzed using an analysis of covariance model with PC\_PN0-12 and PC\_PN0-24 serving as the dependent variable for each respective analysis. Treatment group and the randomization stratification variables will serve as factors and the baseline %PN value will serve as a covariate in each analysis. In each analysis, the higher dose group will be compared to placebo group first. The high-dose comparison will be tested at the 0.025 two-sided significance level at each timepoint. If the high-dose comparison at a particular timepoint is significant at  $p < 0.025$ , then the low-dose comparison with placebo (at the same timepoint) will be tested at the 0.025 level.

For this endpoint, the Type I error rate will be controlled at 0.05 by using a Bonferroni correction for the two timepoints and a step-down procedure to compare each dose group (high dose first, then low dose) with placebo.

#### **Co-Primary Endpoint (responders)**

The continuous responder analysis will be displayed graphically where the  $x$ -axis displays the percent reduction in %PN and the  $y$ -axis shows the proportion of infants who meet each response threshold (from 0 to 100%). The continuous responder curves for each dose vs. placebo will be compared using the Mann Whitney U test based on the 12 week data and another graph and analysis will make the similar comparison at 24 weeks. Each test will be carried out at the 1-sided  $p < 0.10$  significance level.

The trial will have shown benefit if any group comparison stated above is shown to be superior to placebo on both of the co-primary endpoints at the same time (12 or 24 weeks, or both), each at the stated significance level.

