Statistical Analysis of Endpoints	
First Co-Primary Endpoints
 
The primary endpoints (measured at 12 weeks and 24 weeks) will each be analyzed using an analysis of covariance model with PC_PN0-12 and PC_PN0-24 serving as the dependent variable for each respective analysis. Treatment group and the randomisation stratification variables will serve as factors and the baseline %PN value will serve as a covariate in each analysis. In each analysis, the higher dose group will be compared to placebo group first. The high-dose comparison will be tested at the 0.025 two-sided significance level at each timepoint. If the high-dose comparison at a particular timepoint is significant at <math>p < 0.025</math>, then the low-dose comparison with placebo (at the same timepoint) will be tested at the 0.025 level.
 
Second Co-Primary Endpoints
 
The results will be displayed on a graph where the x-axis displays the percent reduction in %PN and the y-axis shows the proportion of infants who meet each response threshold (from 0 to 100%). The continuous responder curves for each dose vs. placebo will be compared using the Mann Whitney U test based on the 12 week data and another graph and analysis will make the similar comparison at 24 weeks. A positive outcome for the continuous responder analyses will be a one-sided p-value less than 0.10.
 
The trial will have shown benefit if any group comparison stated above is shown to be superior to placebo on both of the co-primary endpoints at the same time (12 or 24 weeks, or both), each at the stated significance level.
 
Key Secondary Endpoint
 
The key secondary endpoint will be analyzed using a stratified log-rank test with factors for treatment group and the randomization stratification variables. Separate analyses will be carried out for each dose group. Time to the endpoint will be taken as the 14th day of consecutive less than 10% PN.

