### **3. STUDY DESIGN**

#### **3.1. DESCRIPTION OF STUDY DESIGN**

This multi-center, randomized, double-blind, three-arm, parallel-group trial is designed to assess the efficacy and safety of two doses (4 IU/kg/day and 8 IU/kg/day) of NTRA-9620 compared to matching placebo at two time points (12 and 24 weeks post randomization) administered to infants less than 52 weeks chronological age with SBS (following surgical resection). The study will be conducted at up to 40 clinical trial sites in North America, Europe and Israel. All subjects will be enrolled after their parent(s) or legally authorized guardian(s) sign an IRB/IEC approved informed consent form (ICF). Subjects entering the study will be diagnosed with SBS; they will have at most 70% of their expected bowel length preserved or functioning, requiring PN by intravenous (IV) infusion; they will have a total body weight of at least 500 grams (17.6 ounces) and be at least 28 weeks of gestation in age at the time of entry into the study. At time of study entry, subjects should be able to tolerate at least 10 mL/kg/day of EN but not less than 70% of PN based on caloric intake for at least 7 days.

Each subject, after parent(s) or legal guardian(s) consent to the study, will complete screening assessments. Screening evaluations will include assessment of entry criteria, medical history, as well as a complete physical examination, blood chemistry, hematology and urinalysis evaluations, EKG and concomitant medications.

After meeting all screening and baseline criteria, subjects will be randomized in a 1:1:1 ratio to either 8 IU/kg/day NTRA-9620, 4 IU/kg/day NTRA-9620, or matching placebo. Randomization, which will be performed centrally, will be stratified by estimated percent length of the remaining small intestine ( $L < 50\%$  or  $50\% \leq L \leq 70\%$ ; where L is remaining length of small intestine relative to the expected length for gestational age (13)) and presence or absence of an ileocecal valve. Randomization will take place as close as possible to treatment initiation and not more than 24 hours before the first dose of study medication.

During the 24-week treatment period, subjects are expected to be on PN/IV for all or most of the treatment period and thus are expected to be hospitalized for approximately 12 weeks, but they may be released sooner according to local institution's SOC.

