### **Key Secondary Endpoint**

The key secondary endpoint will be analyzed using a stratified log-rank test with factors for treatment group and the randomization stratification variables. Separate analyses will be carried out for each dose group.

The Statistical Analysis Plan will describe in detail the methods to be used for the primary and key secondary endpoints. The methods will be designed to ensure protection of the Type I error rate across the primary and key secondary endpoints.

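### The responder co-primary is the only confirmatory test that leaves out the randomization strata; if those strata predict outcome, its p-value is conservative.

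*Combined protocol and SAP*

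**What the plan says.** Section 3.1 sets the design: "Randomization, which will be performed centrally, will be stratified by estimated percent length of the remaining small intestine" (below 50% against 50 to 70%) and by "presence or absence of an ileocecal valve". That makes four strata, with 1:1:1 allocation. Section 4.2.3 repeats this.

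Three tests carry the efficacy claims:

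- **ANCOVA on percent change in %PN** (8.1.2, repeated in 8.5.5.1): "Treatment group and the randomization stratification variables will serve as factors", with baseline %PN as covariate, at two-sided 0.025.
- **Responder comparison on the same outcome** (synopsis and 8.1.2): the curves are "compared using the Mann Whitney U test based on the 12 week data", and again at 24 weeks. No stratum or covariate is named. The synopsis adds: "A positive outcome for the continuous responder analyses will be a one-sided p-value less than 0.10". Section 8.5.5.1 gives the level but names no test.
- **Key secondary** (8.1.2 and 8.5.5.2): a "stratified log-rank test with factors for treatment group and the randomization stratification variables".

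The synopsis and 8.1.2 declare benefit only when a dose beats placebo on both co-primaries at one time point. Section 8.1.1 lists bowel length and ileocecal valve among the features of "a population that is expected to have especially high variation with respect to prognosis and therefore to study outcome".

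**The concern.** The Mann-Whitney null variance treats every reshuffling of subjects between the two arms as equally likely. Stratified randomization does not allow that: it keeps the arms nearly balanced within each stratum. If the strata predict outcome, the rank sum varies less from one randomization to the next than the test assumes. The test counts as noise a component that the design has already removed, and its p-value comes out too large.

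At stake are the accuracy of a reported co-primary p-value and a little of that test's power. The plan treats the strata as important enough to adjust the other two tests for them and gives no reason for leaving them out here.

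**Working it through.** **Inputs from the protocol.** One-sided 0.10 (synopsis, 8.1.2); four strata and 1:1:1 allocation (3.1); difference 42 - 30 = 12 points, SD 20, 50 enrolled per arm (8.4).

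**Assumed, because the protocol does not give them.** R2, the share of outcome (rank) variance explained by the strata, from 0 to 0.4; permuted blocks of 6; stratum shares of 15, 20, 25 and 40%; normal outcomes.

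**Step 1: reproduce the stated level.** With 150 subjects, two of the three arms compared and 10,000 simulated trials (Monte Carlo standard error sqrt(0.10 × 0.90 / 10,000) = 0.003), the Mann-Whitney test has level 0.104 when the strata carry no prognosis. Under unstratified randomization it is 0.093 to 0.102 across all R2 values. So 0.10 is what the test delivers when its assumptions hold.

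**Step 2: large-sample level with balanced strata.** The true variance of the rank sum is about (1 - R2) times the variance assumed, so

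level = 1 - Phi(1.2816 / sqrt(1 - R2)).

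- R2 0.1: 1.2816 / 0.9487 = 1.351, level 0.088
- R2 0.2: 1.2816 / 0.8944 = 1.433, level 0.076
- R2 0.4: 1.2816 / 0.7746 = 1.655, level 0.049

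**Step 3: simulation under stratified randomization, no treatment effect.**

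| R2 | Formula | Mann-Whitney | van Elteren |
|---|---|---|---|
| 0 | 0.100 | 0.104 | 0.100 |
| 0.05 | 0.094 | 0.093 | 0.100 |
| 0.10 | 0.088 | 0.092 | 0.098 |
| 0.20 | 0.076 | 0.082 | 0.101 |
| 0.30 | 0.063 | 0.064 | 0.100 |
| 0.40 | 0.049 | 0.052 | 0.100 |

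A further run at about 45 per arm gave about 0.09, 0.076 and 0.06 at R2 0.1, 0.2 and 0.4, with van Elteren at 0.094 to 0.10. Ties from a ceiling at 100% reduction leave the result unchanged: 0.092 at R2 0.1 and 0.064 at R2 0.3.

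**Step 4: effect on the trial's decision.** Power (%) at a difference of 12, SD 20, 4,000 simulated trials per row. The ANCOVA here has the strata but no baseline covariate. The last column pairs it with the unstratified Mann-Whitney test.

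| R2 | Mann-Whitney | van Elteren | ANCOVA | Both co-primaries |
|---|---|---|---|---|
| 0 | 95.2 | 94.4 | 76.65 | 76.63 |
| 0.1 | 96.3 | 96.4 | 80.83 | 80.83 |
| 0.2 | 96.7 | 97.8 | 85.68 | 85.68 |
| 0.3 | 97.1 | 98.6 | 89.93 | 89.90 |

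Joint power cannot exceed ANCOVA power, so in these rows a different rank test could add at most 76.65 - 76.63 = 0.02 or 89.93 - 89.90 = 0.03 of a point. The largest movement in joint power in any run was about half a point. With no treatment effect, the joint rejection rate equalled the ANCOVA rate in every setting.

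**The case against.** The strongest reply is that nothing is broken. A test whose true size is at or below its threshold is valid, the responder test never decides alone, and the ANCOVA decides nearly every case. All of that stands. A reader might infer that the co-primary fails or that false positives rise; the error runs the other way. A reader might also infer that the two co-primaries contradict each other, but no section requires both to adjust for the same factors.

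A second reply is that the shortfall is assumed. This stands in part. A reader might infer that the true level is below 0.10 whatever the data show, and the protocol does not support that. Section 8.1.1 names bowel length and valve alongside age, etiology and feeding regime, and says that total variation is high, not how much these two binary factors explain. High variation from the other sources would lower R2. Against an SD of 20, R2 0.2 implies a between-stratum SD of sqrt(0.2) × 20 = 8.9 points, and R2 0.4 implies 12.6, which is more than the planned effect. At R2 0.05 the level is still about 0.093.

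A third reply is that section 8.1 leaves details to a SAP that overrides the protocol and is not in the supplied text. That SAP may already stratify. But the synopsis and 8.1.2 do not leave the test open: they name one, without strata.

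**Conclusion.** The point holds as a minor, conditional one. Of the three confirmatory tests, only the responder comparison omits the randomization strata. If bowel length and ileocecal valve predict outcome, its one-sided level is about 0.09, 0.08 and 0.05 to 0.06 at assumed R2 of 0.1, 0.2 and 0.4; if they do not, it is 0.10. This rests on near-balance within strata, which stratified randomization implies although no block size is given, and on an R2 that the protocol does not report.

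Stratifying would restore the stated level and, with strata at R2 0.2 or more, add about 1 to 2 points to that test's power. The joint success rule of the synopsis and 8.1.2 would move by at most about half a point. The reason to change is a correct p-value and consistency with the design; a gain in the trial's chance of success is not.

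**What to change.** In the synopsis and in section 8.1.2, replace the Mann-Whitney U test by the van Elteren test stratified by the two randomization factors, at the same one-sided 0.10. Name that test in 8.5.5.1, which now names none. Changing only one of these places would leave the synopsis and the body in disagreement. Keep the responder curves as the display, and note that they pool the strata while the test compares within them.

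The cost is a line of text and code, plus under 1 point of that test's power if the strata are not prognostic (95.2% to 94.4%, a loss of 0.8). Two details need a sentence in the SAP:

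- **Small strata.** The recruitment goal in 4.2.3 is 30 subjects with under 50% of bowel, about 30 / 3 = 10 per arm before the split by valve. The SAP should say how a stratum with subjects in only one of the two compared arms is handled.
- **Imputed data.** Section 8.1.3 imputes missing endpoints, so the SAP should state how the stratified statistic is combined across imputed data sets. The runs above had no missing data.

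If the sponsor prefers the unstratified test, the SAP should give the reason and say that its p-value is conservative when the strata are prognostic.
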